12.4 Data and Safety Monitoring Plan

A comprehensive Data Safety and Monitoring Plan has been submitted by Northwestern University, approved by DCP, and is on file there.

The Participating Organization will be monitored by the Northwestern Cancer Prevention Consortium (NCPC) Research Project Manager. Given the difficulty of planning participant accrual and travel to China, the first monitoring visit will occur approximately after the fifth participant enrolls, with subsequent annual visits. The NCPC will employ an English/Chinese translator to assist with verifying Chinese source documents.

12.5 Sponsor or China Food and Drug Administration Monitoring

The NCI, DCP (or their designee), pharmaceutical collaborator (or their designee), or CFDA may monitor/audit various aspects of the study. These monitors will be given access to facilities, databases, supplies and records to review and verify data pertinent to the study.

12.6 Record Retention

Clinical records for all participants, including CRFs, all source documentation (containing evidence to study eligibility, history and physical findings, laboratory data, results of consultations, *etc.*), as well as IRB/Ethics Committee records and other regulatory documentation, will be retained by the Investigator in a secure storage facility in compliance with HIPAAOffice of Human Research Protections (OHRP), CFDA regulations and guidances, and NCI/DCP requirements,

unless the standard at the site is more stringent. The records for all studies performed in China will be retained for, at minimum, five years after the completion of the research. For NCI/DCP, records will be retained for at least three years after the completion of the research. NCI will be notified prior to the planned destruction of any materials. The records should be accessible for inspection and copying by authorized persons of the China Food and Drug Administration. Because this study is done outside of the United States, applicable regulatory requirements for the China study also apply.

12.7 Cooperative Research and Development Agreement (CRADA)/Clinical Trials Agreement (CTA)

All study agents are to be purchased commercially. No CRADA or CTA is applicable to this study.

13. STATISTICAL CONSIDERATIONS

13.1 Study Design/Description

This is a Phase I, placebo controlled, safety and tolerability study. Randomization is double-blinded. The primary endpoint is clinical safety and tolerability. Secondary endpoints are plasma- and tissue-based measures of inflammation, clinical efficacy, and compliance (via blood drug concentrations).

13.2 Randomization/Stratification

Patients will be randomized by the study statistician. 12 subjects will receive treatment with Berberine and 4 subjects will receive the placebo, in a randomized, double-blinded manner and stratified by gender. Two additional participants are anticipated to be accrued (for a total of 18 subjects) to account for an anticipated dropout rate of 10%. In order to keep the numbers in either treatment group as planned, dropouts in either treatment group will be replaced by subjects assigned to that same treatment and gender group. The ratio of men to women in each treatment group (Berberine/placebo) will be 1:1. The randomization list will be provided by the study statistician to the Investigational pharmacist at Xijing Hospital. Only the Northwestern CRO Quality Assurance Monitors, statistician, and the research pharmacist at Xijing Hospital will know which patient is receiving which treatment.

13.3 Accrual and Feasibility

In a typical month, there are 3-4 subjects identified who would qualify for chemoprevention trials, and about 1/3 of these subjects are agreeable to consider entering trials. We plan to enroll a total of 16-18 subjects (1 treatment arm with 12 subjects and one placebo group with 4 subjects, with 2 additional subjects to account for anticipated attrition; dropouts in either group will be replaced by subjects assigned to that same treatment and gender group). We anticipate this taking about 6-12 months to complete. We also have subjects who participated in prior trials who have provided consent to be contacted for future studies.

13.4 Primary Objective, Endpoint(s), Analysis Plan

Primary Objective: To determine the safety of Berberine administered to patients with UC in clinical remission while receiving maintenance therapy with Mesalamine.

Endpoints: The primary objective will be evaluated by determining whether given subject experiences grade 2 systemic toxicity or not. Upon unblinding the placebo and treatment assignments, relevant counts and rates will be evaluated and reported. Specifically, in addition to assessing clinical toxicity, we will collect tissue and blood samples from recruited participants at the beginning of the trial and at the end of Berberine administration (three months later) and evaluate organ toxicity by standard clinical chemistry tests. Also, we will read tissue samples in China and the US. Finally, we will observe and record symptoms such as fever, fatigue, weight loss, appetite, stool frequency, bloody stool and other upper and lower gastrointestinal tract symptoms in participants.

Analysis: We plan to recruit 12 treatment and 4 placebo subjects for a total of 16 evaluable subjects. With potential dropout of 2 subjects we plan to recruit a total of 18 subjects. Dropouts in either treatment group will be replaced by subjects assigned to that same treatment and gender group. We do not expect to see any toxicity in either group of

patients; in fact we believe the underlying toxicity rate is the same in both groups. With no observed toxicities, we will be able to establish an approximate 95% upper bound on Prob(Tox) as the “Rule of Three”: $3/(n+1)$ or $3/17 = 0.18$ for both groups and $3/13 = 0.23$ for the treatment group⁴³. Other statistical analysis will consist of providing descriptive statistics (mean, SD, max, min) on patient characteristics and on toxicity rates; in case no events occur, appropriate methods will be used, such as the Rule of Three above for upper confidence bound, continuity correction or exact confidence bounds for two-sided intervals.

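### Does the primary toxicity endpoint lose its confidence bound as soon as one event occurs?

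*Combined protocol and SAP*

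**What the plan says.** Section 13.4 evaluates the primary objective by "determining whether given subject experiences grade 2 systemic toxicity or not". After unblinding, "relevant counts and rates will be evaluated and reported". The planned size is 12 Berberine and 4 placebo subjects, 16 evaluable in all.

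Precision is then described in two places. The first reads "With no observed toxicities, we will be able to establish an approximate 95% upper bound on Prob(Tox", followed by the Rule of Three, 3/(n+1), evaluated as "or $3/17 = 0.18$ for both groups and $3/13 = 0.23$ for the treatment group". Just before this, the authors state their belief about the two arms: "in fact we believe the underlying toxicity rate is the same in both groups". The second place promises "providing descriptive statistics (mean, SD, max, min) on patient characteristics and on toxicity rates" and, after a semicolon, adds "in case no events occur, appropriate methods will be used, such as the Rule of Three above for upper confidence bound". That clause ends by naming "continuity correction or exact confidence bounds for two-sided intervals".

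Nothing else in Section 13 supplies an interval for toxicity. The confidence intervals in Section 13.5 concern plasma biomarkers, Section 13.7 sets the observation window, and Section 13.9 only refers back.

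**The concern.** Both mentions of a toxicity bound are conditional on zero events. If one or more subjects have a grade 2 toxicity, the text leaves counts, rates and a list of summary statistics (mean, SD, maximum, minimum) that suits continuous characteristics better than a yes/no outcome. The upper bound is the only statement of precision for the primary endpoint, so it appears to lapse in the case where a reader would most want it.

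That case is not far-fetched. Section 5.6 sets out what happens when grade 2 toxicity occurs, so the protocol itself allows for it. At this sample size the interval also depends on the method, and an unstated method leaves room to choose after unblinding. A second worry is that the pooled figure of 0.18 might be taken as a bound for Berberine alone.

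**Working it through.** **Inputs from Section 13.4.** Yes/no endpoint; n = 12 Berberine, n = 4 placebo, n = 16 together; approximate 95% upper bound at zero events by 3/(n+1).

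**1. The plan's own figures.**
- Both groups: 3/17 = 0.176, stated as 0.18.
- Berberine: 3/13 = 0.231, stated as 0.23.
- Exact one-sided 95% bound at zero events, 1 − 0.05^(1/n): 0.171 for n = 16 and 0.221 for n = 12.

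The stated figures reproduce and lie slightly above the exact ones. The exact two-sided 95% upper limit at 0 of 12 is 1 − 0.025^(1/12) = 0.265. That is not a rival to 0.23, because it is the limit of a two-sided interval; the like-for-like pair is 0.231 and 0.221.

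**2. How likely is the case the wording leaves out?** P(at least one event in 12) = 1 − (1 − p)^12. The documents give no grade 2 rate, so p is assumed:

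| Assumed true rate | P(≥1 event in 12) |
|---|---|
| 0.01 | 0.114 |
| 0.05 | 0.460 |
| 0.10 | 0.718 |

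The chance passes one half at p = 1 − 0.5^(1/12) = 0.056.

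**3. What the exact method named in the plan gives once events occur.** The one-sided 95% upper bound for x events in n is the 95th percentile of Beta(x+1, n−x). For n = 12:

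| Events | One-sided 95% upper bound | Two-sided 95% interval |
|---|---|---|
| 0 | 0.221 | 0 to 0.265 |
| 1 | 0.339 | 0.002 to 0.385 |
| 2 | 0.438 | 0.021 to 0.484 |
| 3 | 0.527 | 0.055 to 0.572 |

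The method carries over to any count with no new assumption.

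**4. Could one event look better than none?** For 1 of 12 the rate is 0.0833 and its standard error is √(0.0833 × 0.9167/12) = 0.0798.
- Uncorrected normal, one-sided: 0.0833 + 1.645 × 0.0798 = 0.215, below the 0.23 stated for zero events.
- With the continuity correction 1/(2 × 12) = 0.0417: 0.0833 + 0.1313 + 0.0417 = 0.256, above 0.23.
- Exact: 0.339, above 0.23.

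The paradox arises only with the uncorrected normal interval, which the plan nowhere proposes. Both methods that it does name put one event above zero events.

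**5. The pooled 0.18.** As a bound on a rate common to both arms, 3/17 has confidence 1 − (14/17)^16 = 0.955. As a bound on Berberine alone with a placebo rate of zero, it has 1 − (14/17)^12 = 0.903. The plan labels 0.18 as covering both groups, states the equal-rates belief, and prints 0.23 for the treatment group in the same sentence. It does not offer 0.18 as a Berberine-only bound.

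**The case for a change.** The strongest case for a change is that a plan should not rely on readers looking past its own conditional clause. Even on the generous reading, Section 13.4 offers two methods without choosing between them and gives no confidence level for the two-sided interval. At 1 of 12 the choice matters: the one-sided upper bound is 0.256 with continuity correction and 0.339 exact. One sentence would settle it at no cost in patients or data.

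The literal gap stands, and so does the dependence on method. The consequence is small, though. Neither continuity correction nor an exact bound is peculiar to zero events, so their appearance in that sentence suggests the authors had wider use in mind, although the text does not say so. Counts and rates are to be reported after unblinding, so a choice of method could not hide the data: anyone with 1 of 12 in hand can compute the exact interval. No hypothesis test or go/no-go rule in Section 13 uses the bound, and the dose changes in Section 5.6 act on individual subjects.

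The protocol also contradicts itself on whether dropouts are replaced (Sections 3, 5.1, 13.2, 13.3 and 13.4 say yes; Sections 5.7, 8.3 and 13.6 say no). That affects the denominator of any toxicity rate, whatever interval is used. It is a separate matter and does not bear on whether a bound is planned.

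**Conclusion.** No change is needed. As worded, Section 13.4 mentions toxicity bounds only for zero events, and no other section supplies one for a positive count. That is missing detail rather than an error. Followed as written, the plan still reports correct counts and rates, its stated 0.18 and 0.23 are correctly computed and labelled, and it names an exact method that an analyst would apply as a matter of course. For the Berberine arm that means one-sided 95% upper bounds of 0.22, 0.34, 0.44 and 0.53 for 0, 1, 2 and 3 events.

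These figures assume 12 evaluable Berberine subjects. The chance that the uncovered case arises, 11% to 72%, rests on assumed true rates of 1% to 10%. Even near the top of that range the conclusion holds, because the bound feeds no decision and can be recovered from the reported counts. Which of 0.18 and 0.23 should lead the report is a matter of preference.

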13.5 Secondary Objectives, Endpoints, Analysis Plans

Secondary Objectives: To determine the efficacy of Berberine and compliance of subjects.

Endpoints and Analyses:

- For plasma biomarkers, we will use descriptive statistics and graphical methods to present the evidence of possible correlations in outcomes of interest. Box plots and confidence intervals will be used to assign proper mass weight to groups of observations. “Before” and “after” intervention values and their difference will be compared with suitably chosen counterparts.
- Colorectal tissue IHC biomarkers and DNA methylation status for SFRP1, TCERGIL, FBN2 and TFP12 will be measured twice, before and after the treatment, and their difference will be studied in relative to values in their respective control groups. The Ki-67 and cleaved caspase 3 outcomes will be the number of cells positive over total number. The TNFa, COX-2, and NF- κ B immunohistochemistry will be done by quantitation through chromovision and will be expressed as % of control (placebo, pre-treatment). The description and comparison of biomarkers and gene methylation status will be performed both with the view of Before – After possible change within each treatment group, as well as with the view of Treatment - Control groups for Before and for the After period. Descriptive statistics and graphical methods will be performed to present the evidence of possible correlations in outcomes of interest. Tissue biomarkers will be measured in China and separately in the US. Comparisons of before and after treatment will be performed separately as a function of country, and then differences between countries will be compared. This will be done with the purpose of gaining knowledge of the range of changes to plan future studies in these markers.
- Blood drug concentration will be measured before and after 3 months treatment. Comparisons of before and after treatment will be performed.

13.6 Reporting and Exclusions

Compliance will be formally assessed by clinical visit and pill counts each month, and by measuring blood drug concentrations at the end of the study. Patients will be considered compliant if they have taken 80% of their study agent doses as directed. During the first month of study, patients will be counseled regarding the importance of taking all doses, but will not be removed from the study for missing doses, unless 10 consecutive days are missed. Patients who are found to be non-compliant at the monthly assessments will be kept in the study; their information will be used in the final ‘intent to treat’ analysis, which will contain all randomized patients.

We expect that of 18 recruited participants, all will have complete data; it is possible that up to 10% of participants drop out. Participants will not be replaced. Analysis will be based upon complete data.

13.7 Evaluation of Toxicity

All participants will be evaluated for toxicity from the time of their first dose of Berberine through day 120 (corresponding to one month after completing the 90 day treatment period).

13.8 Evaluation of Response

All participants included in the study will be assessed for response to intervention, even if there are major protocol deviations or if they are ineligible. All of the participants who met the eligibility criteria (with the possible exception of those who did not receive study agent) will be included in the main analysis. All conclusions regarding efficacy will be based on all eligible participants. Refer to section 13.5 for information on evaluation of response.

13.9 Interim Analysis

Toxicity will be evaluated continuously as outlined above.

13.10 Ancillary Studies

N/A

14. ETHICAL AND REGULATORY CONSIDERATIONS

14.1 Form FDA 1572

Prior to initiating this study, the Protocol Lead Investigator at the Lead or Participating Organization(s) will provide a signed Form FDA 1572 stating that the study will be conducted in compliance with regulations for clinical investigations and listing the investigators, at each site that will participate in the protocol. All personnel directly involved in the performance of procedures required by the protocol and the collection of data should be listed on Form FDA 1572.

14.2 Other Required Documents

14.2.1 Signed and dated current (within two years) CV or biosketch (translated into English, if necessary) for all study personnel listed on the Form FDA 1572 and Delegation of Tasks form for the Lead Organization and all Participating Organizations.

14.2.2 Current medical licenses (where applicable, and translated into English, if necessary) for all study personnel listed on Form FDA 1572 and Delegation of Tasks form for the Lead Organization and all Participating Organizations.

14.2.3 Lab certification (e.g., CLIA, CAP, and translated into English, if necessary) and lab normal ranges (translated into English, if necessary) for all labs listed on Form FDA 1572 for the Lead Organization and all Participating Organizations.

14.2.4 Documentation of training in “Protection of Human Research Subjects” for all study personnel listed on the FDA Form 1572 and Delegation of Tasks form for the Lead Organization and all Participating Organizations will be obtained. For personnel in China, each certificate of human subjects' protection training will be obtained but will not be translated into English. Instead, we will obtain a letter, in English, on Xijing Hospital letter head and signed by the Ethics Committee, listing the names of the study personnel who have completed this training.

14.2.5 Documentation of Federalwide Assurance (FWA) number for the Lead Organization and all Participating Organizations.

14.2.6 Signed Package Insert acknowledgement form

14.2.7 Delegation of Tasks form for the Lead Organization and all Participating Organizations signed by the Principal Investigator for each site and initialed by all study personnel listed on the form

14.2.8 Signed and dated NCI, DCP Financial Disclosure Form for all study personnel listed on Form FDA 1572 for the Lead Organization and all Participating Organizations

14.3 Institutional Review Board Approval

Prior to initiating the study and receiving agent, the Investigators at the Lead Organization and the Participating Organization(s) must obtain written approval to conduct the study from the appropriate IRB/Ethics Committee. Should changes to the study become necessary, protocol amendments will be submitted to the DCP PIO according to DCP Amendment Guidelines. The DCP-approved amended protocol must be approved by the IRB/Ethics Committee prior to implementation. Ethics Committee approvals and Informed Consent documents in Chinese will be translated into English as part of the site essential regulatory documents.

14.4 Informed Consent

All potential study participants will be given a copy of the IRB/Ethics Committee-approved Informed Consent to review. The investigator will explain all aspects of the study in lay language and answer all questions regarding the study. If the participant decides to participate in the study, he/she will be asked to sign and date the Informed Consent document. The study agent(s) will not be released to a participant who has not signed the Informed Consent document. Subjects who refuse to participate or who withdraw from the study will be treated without prejudice.

Participants must be provided the option to allow the use of blood samples, other body fluids, and tissues obtained during testing, operative procedures, or other standard medical practices for further research purposes. If applicable, statement of this option may be included within the informed consent document or may be provided as an addendum to the consent. A Model Consent Form for Use of Tissue for Research is available through a link in the DCP website.

Prior to study initiation, the informed consent document must be reviewed and approved by NCI, DCP, the Consortium Lead Organization, and the IRB at each Organization at which the protocol will be implemented. Any subsequent changes to the informed consent must be approved by NCI, DCP, the Consortium Lead Organization's IRB, and then submitted to each organization's IRB for approval prior to initiation. Ethics Committee approvals and Informed Consent documents in Chinese will be translated into English as part of the site essential regulatory documents.

14.6 Other

This trial will be conducted in compliance with the protocol, Good Clinical Practice (GCP), and the applicable regulatory requirements.

APPENDIX A
Ulcerative Colitis Disease Activity Index (UCDAI)

1. Stool Frequency*	Score
Normal number of stools/day for this patient	0
1–2 Stools/day>normal	1
3–4 Stools/day>normal	2
>4 Stools/day>normal	3
2. Rectal Bleeding†	Score
No blood seen	0
Streaks of blood with stool less than half of the time	1
Obvious blood with stool most of the time	2
Blood alone passed	3
3. Endoscopic Findings	Score
Normal or inactive disease	0
Mild disease (erythema, decreased vascular pattern, mild friability)	1
Moderate disease (marked erythema, absent vascular pattern, friability, erosions)	2
Severe disease (spontaneous bleeding, ulceration)	3
4. Physician's Global Assessment‡	Score
Normal	0
Mild disease	1
Moderate disease	2
Severe disease	3
UCDAI = total score	

* Each patient serves as his or her own control to establish the degree of abnormality of the stool frequency

† The daily bleeding score represents the most severe bleeding of the day

‡ The physician's global assessment acknowledges the 3 other criteria, as well as the patient's daily recall of abdominal discomfort, general sense of well-being, and other observations such as physical findings and the patient's performance status

APPENDIX B
Select CYP450 Inducers, Inhibitors, and Substrates

	1A2	2C19	2D6	3A4
Inducers	ritonavir rifampin phenytoin omeprazole phenobarbital nicotine	rifampin carbamazepine ritonavir efavirenz	rifampin phenytoin phenobarbital carbamazepine	efavirenz, nevirapine, rifampin, phenytoin, phenobarbital, carbamazepine, glucocorticoids, St. John's Wort, ritonavir, etravirine
Inhibitors	fluoroquinolones cimetidine ticlopidine fluvoxamine amiodarone atazanavir	cimetidine ketoconazole omeprazole fluoxetine lansoprazole paroxetine etravirine	ritonavir paroxetine sertraline fluoxetine cimetidine celecoxib amiodarone quinidine methadone	ritonavir, indinavir, nelfinavir, amprenavir, atazanavir, saquinavir, delavirdine, fluconazole, ketaconazole, itraconazole, amiodarone, diltiazem, fluvoxamine, nefazodone, fluoxetine, clarithromycin, erythromycin, posaconazole, grapefruit juice, Seville orange juice
Substrates	haloperidol theophylline zileuton amitriptyline cyclobenzaprine olanzapine	nelfinavir lansoprazole omeprazole pantoprazole diazepam phenytoin voriconazole etravirine	metoprolol carvedilol codeine dextrometh- orphan tramadol venlafaxine	clarithromycin, cyclosporine, erythromycin, alprazolam, midazolam, triazolam, simvastatin, lovastatin, atorvastatin, nifedipine, nisoldipine, felodipine, PIs, nevirapine, efavirenz (2B6>3A4), delavirdine, sertraline, bepridil, propafenone, amiodarone, flecainide, irinotecan, pimozide, ergotamine, etravirine, maraviroc

*Table provided by <http://www.hivguidelines.org/clinical-guidelines/adults/hiv-drug-drug-interactions/#APPENDIX%20A.%20ROUTES%20OF%20ELIMINATION%20OF%20HAART%20AND%20THE%20EFFECT%20ON%20CYP450>

